1.1. Synopsis

Protocol Title: Bioequivalence of Lasmiditan Oral Disintegrating Tablet Compared to Current Immediate-Release Tablet Formulation to Support Treatment of Migraine

Short Title: Bioequivalence of lasmiditan oral disintegrating tablet compared to current immediate-release tablet formulation to support treatment of migraine.

Rationale: Previous clinical studies of lasmiditan have used an immediate-release (IR) tablet formulation. An oral-disintegrating (OD) tablet has been developed to aid pediatric development and for more convenient administration in adults, e.g., for those who have difficulty swallowing a tablet. This study is intended to determine the bioequivalence, safety, and tolerability of a newly developed OD tablet of lasmiditan compared to the current IR tablet.

Objectives and Endpoints

Objectives	Endpoints
Primary	

 To evaluate the PK of lasmiditan following administration of a single 100-mg dose of lasmiditan OD tablet (test) administered without water versus the current IR tablet formulation (reference) in healthy participants 	
 C_{max}, $AUC(0-\infty)$, and $AUC(0-t_{last})$
Secondary	
 C_{max}, $AUC(0-\infty)$, and $AUC(0-t_{last})$ Incidence of TEAEs and SAEs

Abbreviations: $AUC(0-\infty)$ = area under the concentration versus time curve from time zero to infinity; $AUC(0-t_{last})$ = area under the concentration time curve from time zero to time t , where t is the last time point with a measurable concentration; C_{max} = maximum observed drug concentration; IR = immediate release; OD = oral disintegrating; PK = pharmacokinetics; SAE = serious adverse event; TEAE = treatment-emergent adverse event.

Overall Design**Screening**

All participants will be screened within 28 days prior to enrollment.

Treatment and Assessment Period

Eligible participants will take part in 3 separate dosing periods. In each period, participants will be admitted to the clinical research unit (CRU) on Day -1 and remain resident in the CRU until discharge on Day 6.

There will be a washout period of ≥ 5 days between the day of dosing in 1 period and the day of dosing in the subsequent period. Days 5 and 6 of Period 1 and 2 may coincide with Days -1 and 1 of Period 2 and 3, respectively, provided the required washout between lasmiditan doses is observed.

On Day 1 of Period 1, participants will be equally randomized to receive a 100-mg oral dose in 1 of 6 dosing sequences in each of 3 dosing periods.

Pharmacokinetic blood sampling and safety assessments, including vital sign measurements, physical examinations, clinical laboratory tests, electrocardiograms, and adverse event recording will be performed according to the Schedule of Activities.

Follow-up

Day 6 of Period 3 will be considered the final visit of the study.

Disclosure Statement: This is a Phase 1, open-label, randomized, single-dose, 3-way crossover study, with 6 sequences in healthy participants.

Number of Participants: Approximately 48 participants will be enrolled to ensure that 36 participants, 6 per treatment sequence, complete the study.

Intervention Groups and Duration: Participants will receive single 100-mg doses of lasmiditan in each of 3 dosing periods, according to 1 of the randomized sequences detailed below.

Dosing Sequences for Protocol H8H-MC-LAIA

[figure not shown]
Sequence	Period 1	Period 2	Period 3
1	IR (reference)	OD without water (test)	OD with water (test)
2	IR (reference)	OD with water (test)	OD without water (test)
3	OD without water (test)	OD with water (test)	IR (reference)
4	OD without water (test)	IR (reference)	OD with water (test)
5	OD with water (test)	IR (reference)	OD without water (test)
6	OD with water (test)	OD without water (test)	IR (reference)

Abbreviations: IR = immediate release; OD = oral disintegrating.

Screening will occur up to 28 days prior to enrollment. Each participant will take part in 3 treatment periods. In each period, participants will be admitted to the CRU on Day -1 and remain resident in the CRU until discharge on Day 6. At the discretion of the investigator, participants may remain resident in the CRU for the entirety of the study, i.e., from admission to the CRU on Day -1 of Period 1 until discharge from the CRU on Day 6 of Period 3, after all assessments have been completed.

Data Monitoring Committee: No

1.2. Schema

* Days 5 and 6 may be equivalent to Days -1 and 1, respectively, for the next treatment period if a minimum of 5 days between lasmiditan doses is observed

1.3. Schedule of Activities (SoA)

Study Schedule Protocol H8H-MC-LAIA

Procedure	Screening	Dosing Periods 1 to 3								Comments
	-28 to -2 days prior to D1	D-1 ^a	D1 ^a	D2	D3	D4	D5 ^a	D6 ^a	ED	
Informed consent	X									
Admission to CRU		X								Participants may remain at the CRU throughout the duration of the study, at the discretion of the investigator, i.e., admission to CRU in Period 1 only.
Discharge from CRU								X		Participants may remain at the CRU throughout the duration of the study, at the discretion of the investigator, i.e., discharge from CRU in Period 3 only.
Medical history and demographics	X									
Participant eligibility	X									Confirm participant eligibility against inclusion and exclusion criteria (see Section 5).
Lasmiditan administration			X							A minimum washout of 5 days between lasmiditan doses is required.
Height	X									
Weight	X									
Urine drug screen	X	X								On D-1, only required if participant is being admitted to CRU.
Alcohol breath test	X	X								On D-1, only required if participant is being admitted to CRU.
Pregnancy test	X	X								Serum pregnancy test to be performed at screening. Urine pregnancy test to be performed on D-1 (admission to CRU only).
Supine vital signs (pulse rate, blood pressure, and oral body temperature)	X	X	P, 1, 2 h	24 h					X	Time points may be added for each period, if warranted and agreed up on between Lilly and the investigator.
12-lead ECG	X		P							

Procedure	Screening	Dosing Periods 1 to 3								Comments
		D-1 ^a	D1 ^a	D2	D3	D4	D5 ^a	D6 ^a	ED	
Clinical laboratory tests	X	X		24 h					X	See Appendix 2 (Section 10.2) for details.
Full physical examination	X									Additional symptom-driven physical examinations may be performed at the discretion of the investigator.
Pharmacogenetic blood sample			P							D1 of Period 1 only.
PK sampling in plasma (lasmiditan and M8)			P, 0.5, 1, 1.5, 2, 2.5, 3, 4, 6, 8, 12 h	24 h	48 h	72 h	96 h	120 h		The 120 h sample may serve as the D1 predose sample for subsequent periods, if participants are remaining in-house.
Product acceptability and palatability			X							D1 of dosing periods when the OD tablet is administered either with or without water. Complete questionnaire immediately after OD tablet administration.
Adverse event review	X	X	X	X	X	X	X	X	X	
Concomitant medication review	X	X	X	X	X	X	X	X	X	

Abbreviations: CRU = clinical research unit; ECG = electrocardiogram; D = Day; ED = early discontinuation; h = hour; M8 = metabolite 8; OD = oral disintegrating; P = predose; PK = pharmacokinetic(s).

^a The Day 5 and Day 6 visits of a treatment period may occur at the same time as the Day -1 and Day 1 visits, respectively, of the subsequent treatment period. Therefore, assessments that occur on both visits will only be performed once. All results must be reviewed prior to dosing on Day 1 of each treatment period. The Day 6 visit of Treatment Period 3 will be considered the final visit.

2. Introduction

Lasmiditan (LY573144) has been developed by Eli Lilly and Company (Lilly), and approved by the Food and Drug Administration (FDA), for the acute treatment of migraine with or without aura in adults. Full details of the preclinical and clinical safety and tolerability data are contained in the Investigator's Brochure (IB).

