4.1. Overall Design

Study H8H-MC-LAIA (LAIA) is a Phase 1, open-label, randomized, single-dose, 3-way crossover study in healthy participants. Approximately 48 participants will be enrolled such that 36 participants, 6 per treatment sequence, complete the study.

Screening

All participants will be screened within 28 days prior to enrollment.

Treatment and Assessment Period

Eligible participants will take part in 3 separate dosing periods. In each period, participants will be admitted to the CRU on Day -1 and remain resident in the CRU until discharge on Day 6. At the discretion of the investigator, participants may remain resident in the CRU for the entirety of the study, i.e., from admission to the CRU on Day -1 of Period 1 until discharge from the CRU on Day 6 of Period 3, after all assessments have been completed.

There will be a washout period of ≥ 5 days between the day of dosing in 1 period and the day of dosing in the subsequent period. Days 5 and 6 of Period 1 and 2 may coincide with Days -1 and 1 of Period 2 and 3, respectively, provided the required washout between lasmiditan doses is observed.

On Day 1 of Period 1, participants will be equally randomized to receive a 100-mg oral dose in 1 of 6 dosing sequences in each of 3 dosing periods as shown in [Table LAIA.1](#).

Table LAIA.1. Dosing Sequences for Protocol H8H-MC-LAIA

Sequence	Period 1	Period 2	Period 3
1	IR (reference)	OD without water (test)	OD with water (test)
2	IR (reference)	OD with water (test)	OD without water (test)
3	OD without water (test)	OD with water (test)	IR (reference)
4	OD without water (test)	IR (reference)	OD with water (test)
5	OD with water (test)	IR (reference)	OD without water (test)
6	OD with water (test)	OD without water (test)	IR (reference)

Abbreviations: IR = immediate release; OD = oral disintegrating.

Pharmacokinetic blood sampling and safety assessments, including vital sign measurements, physical examinations, clinical laboratory tests, electrocardiograms (ECGs), and AE recording will be performed according to the SoA (Section [1.3](#)).

Follow-up

Day 6 of Period 3 will be considered the final visit of the study.

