7.2. Participant Discontinuation/Withdrawal from the Study

A participant may withdraw from the study:

- at any time at his/her own request
- at the request of his/her designee (for example, parents or legal guardian)
- at the discretion of the investigator for safety, behavioral, compliance, or administrative reasons
- if the participant becomes pregnant during the study
- if enrollment in any other clinical study involving an investigational product or enrollment in any other type of medical research judged not to be scientifically or medically compatible with this study.

Discontinuation is expected to be uncommon.

At the time of discontinuing from the study, if possible, an early discontinuation visit should be conducted, as shown in the SoA (Section 1.3). See SoA for data to be collected at the time of study discontinuation and follow-up and for any further evaluations that need to be completed. The participant will be permanently discontinued both from the study intervention and from the study at that time.

If the participant withdraws consent for disclosure of future information, the sponsor may retain and continue to use any data collected before such a withdrawal of consent. If a participant withdraws from the study, he/she may request destruction of any samples taken and not tested, and the investigator must document this in the site study records.

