8.3.5. Pregnancy

Details of all pregnancies in female participants and female partners of male participants will be collected after the start of study intervention and until study end.

If a pregnancy is reported, the investigator should inform the sponsor within 24 hours of learning of the pregnancy and should follow the procedures outlined in Appendix 4 (Section 10.4).

Abnormal pregnancy outcomes (e.g., spontaneous abortion, fetal death, stillbirth, congenital anomalies, ectopic pregnancy) are considered SAEs.

Pregnancy (maternal or paternal exposure to study intervention) does not meet the definition of an AE. However, to fulfill regulatory requirements, any pregnancy should be reported following the SAE process described in Appendix 3 (Section 10.3) to collect data on the outcome for both mother and fetus.

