10.2. Appendix 2: Clinical Laboratory Tests

The tests detailed below will be performed by the local laboratory.

Protocol-specific requirements for inclusion or exclusion of participants are detailed in Section [5](#) of the protocol.

Additional tests may be performed at any time during the study as determined necessary by the investigator or required by local regulations.

Pregnancy testing will be conducted as detailed in the SoA (Section [1.3](#)).

Investigators must document their review of each laboratory safety report.

Clinical Laboratory Tests

Hematology	Clinical Chemistry
Hematocrit	Sodium
Hemoglobin	Potassium
Erythrocyte count (RBC)	Bicarbonate
Mean cell volume	Chloride
Mean cell hemoglobin	Calcium
Mean cell hemoglobin concentration	Phosphorus/Phosphate
Leukocytes (WBC)	Glucose (fasting)
Platelets	Blood urea nitrogen
Differential WBC (absolute counts and %) of:	Creatinine
Neutrophils	Uric acid
Lymphocytes	Total protein
Monocytes	Albumin
Eosinophils	Total bilirubin ^a
Basophils	Alkaline phosphatase
Urinalysis	Aspartate aminotransferase
Specific gravity	Alanine aminotransferase
pH	Ethanol testing ^b
Protein	Urine drug screen ^b
Glucose	Hepatitis B surface antigen ^c
Ketones	Hepatitis C antibody ^{c,d}
Bilirubin	HIV ^c
Urobilinogen	Serum pregnancy test (all females) ^c
Blood	Urine pregnancy test (all females) ^e
Nitrite	FSH (postmenopausal females only) ^c
Microscopic examination of sediment ^f	

Abbreviations: FSH = follicle-stimulating hormone; HIV = human immunodeficiency virus; RBC = red blood cells; WBC = white blood cells.

Note: Results of these assays will be validated by the local laboratory at the time of testing. Additional tests may be performed or auto-calculated by the laboratory as part of its standard panel that cannot be removed. Some of the above parameters are calculated from measured values. Omission of calculated values will not be considered as a protocol violation.

- ^a Direct and indirect bilirubin will be analyzed if total bilirubin is elevated.
- ^b Performed at screening and admission to the clinical research unit (CRU; Day -1).
- ^c Performed at screening only.
- ^d Participants with a positive hepatitis C antibody test result can have a confirmatory hepatitis C RNA test.
- ^e Performed for all females on admission to CRU (Day -1). A positive urine test will be confirmed with a serum pregnancy test.
- ^f Test only if dipstick result is abnormal.

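### A woman kept resident throughout has one scheduled urine pregnancy test, on Day -1 of Period 1, so doses 2 and 3 follow it by at least 6 and 11 days with no planned retest

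*Protocol*

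**What the plan says.** The pregnancy row of the Schedule of Activities (SoA, Protocol Section 1.3) is marked at screening, for a serum test, and at Day -1, for a urine test. Its comment restricts the second: "Urine pregnancy test to be performed on D-1 (admission to CRU only". Appendix 2 (Section 10.2) repeats the restriction in footnote e, "Performed for all females on admission to CRU (Day -1", and footnote c confines the scheduled serum test to screening.

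Section 4.1 describes the default stay in each period: "participants will be admitted to the CRU on Day -1 and remain resident in the CRU until discharge on Day 6". It also lets the investigator keep participants in the unit for the entire study. For them the SoA admission row says "i.e., admission to CRU in Period 1 only". The schema note in Section 1.2 explains how periods can run together: "Days 5 and 6 may be equivalent to Days -1 and 1, respectively, for the next treatment period", given at least 5 days between doses.

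On pregnancy after dosing has begun, Section 7.2 lists as a ground for withdrawal "if the participant becomes pregnant during the study". Section 10.4.4 requires study intervention to be discontinued in a participant who becomes pregnant. Section 8.3.5 adds: "Details of all pregnancies in female participants and female partners of male participants will be collected after the start of study intervention", until the study ends.

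**The concern.** The protocol treats further exposure during pregnancy as something to prevent, but whether a woman is retested before doses 2 and 3 depends on where she sleeps between periods. That is an operational decision left to the investigator.

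Confinement makes a new conception during the stay unlikely. It does nothing about a conception shortly before admission that is still undetectable on Day -1 of Period 1. Such a pregnancy could become detectable before dose 2 or dose 3, and no scheduled test would find it.

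What is at stake is one or two avoidable doses in a healthy volunteer who, by Section 2.3, can expect no therapeutic benefit. A retest could not prevent dose 1. Nothing in the bioequivalence comparison depends on this point.

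**Working it through.** **Inputs**

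- Urine test: Day -1, at admission only (SoA pregnancy row; Appendix 2, footnote e).
- Admissions for a participant resident throughout: 1 (SoA admission row).
- Doses: 3, on Day 1 of each period (Section 4.1).
- Interval between doses, W: at least 5 days (Section 4.1; SoA).
- Discharge and final visit: Day 6 (Section 4.1; SoA).

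**Day numbering.** Day 6 − Day 1 = 5 days = 120 h. This agrees with the 5-day minimum and with the SoA note that the 120 h sample may serve as the next predose sample. Because Days 5 and 6 can coincide with the next Days -1 and 1, Day -1 is the calendar day before Day 1.

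**Days from the last scheduled urine test to each dose.** Put Day -1 of Period 1 at t = 0. Doses fall at t = 1, 1 + W and 1 + 2W. A resident woman's only test is at t = 0, so these are also her intervals. A readmitted woman is tested on each Day -1, so hers are always 1.

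| W (days) | Resident: doses 1, 2, 3 | Readmitted: doses 1, 2, 3 |
|---|---|---|
| 5 | 1, 6, 11 | not possible |
| 6 | 1, 7, 13 | 1, 1, 1 |
| 7 | 1, 8, 15 | 1, 1, 1 |

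**Why readmission needs W ≥ 6.** The next dose falls on Day W + 1 of the current period, so the next Day -1 is Day W. Discharge is on Day 6. At W = 5 the next Day -1 comes before discharge. At W = 6 discharge and readmission share a day, and at W = 7 there is one night out.

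**To the final visit.** Day 6 of Period 3 is 5 days after dose 3: 1 + 2W + 5 = 16 days after the single test at W = 5.

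**Precision.** These are calendar days. If the Day -1 test is taken 12 to 24 h before dose 1, the elapsed times to doses 2 and 3 at W = 5 are 5.5 to 6.0 and 10.5 to 11.0 days.

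**Could another scheduled test fill the gap?** The SoA plans clinical laboratory tests on Day -1 and at 24 h in each period. Section 10.2.1 agrees: 6 samples = 2 per period × 3 periods. The panel includes urinalysis, but Appendix 2 limits both pregnancy tests to screening or admission. The pregnancy row is not marked at early discontinuation either. A resident woman therefore has no scheduled pregnancy test from dose 1 to the final visit.

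**The case against.** The strongest reply is that the schedule is deliberate and consistent. The urine drug screen and alcohol breath test are also limited on Day -1 to participants being admitted, on the sensible principle that only people who have been outside need rechecking. Section 5 says eligibility criteria are not applied continuously, and exclusion criterion 23 refers to screening and admission. Section 10.4.2.1 asks for a negative urine test within 24 hours before exposure, but in a sentence about starting treatment, so it is met at dose 1. All of this stands: no protocol rule is broken. The principle fits drugs and alcohol better than pregnancy, however, because confinement controls new intake but cannot reveal a conception that preceded it.

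Second, the stop rule does not need a scheduled test. Pregnancy may come to light through daily adverse event review or through an additional test, which Appendix 2 allows at any time. That is true, but neither is a planned pregnancy check.

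Third, a conception before admission sits at the edge of rules about becoming pregnant during the study; it falls within them only if it followed consent. Entry already has two tests, contraception is required (Section 10.4.2.1), and criterion 24 excludes women planning pregnancy. The documents give no detection lag and show no added harm from doses 2 and 3 beyond dose 1. These points keep the matter small.

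Last, retesting each Day -1 still leaves every woman, resident or readmitted, without a scheduled test for the 1 + 5 = 6 days from Day -1 of Period 3 to the final visit. That is correct. The change protects doses 2 and 3; it does not provide an end-of-study check.

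**Conclusion.** The point holds as a low-probability gap in participant safety, and acting on it is optional. A woman kept resident has one scheduled urine pregnancy test, and doses 2 and 3 follow it by at least 6 and 11 calendar days. A readmitted woman is tested the day before each dose.

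These intervals describe the schedule; they are not a measure of risk. The number of affected women cannot be derived, because the documents do not give the number of women, the share kept resident or the detection lag of the test. Given the contraception rule and criterion 24, it should be very small. The conclusion assumes that the admission restriction is applied as written and that no discretionary test is done.

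**What to change.** In the SoA pregnancy row, delete the parenthesis that limits the urine test to CRU admission. Amend Appendix 2 footnote e so that the test is done on Day -1 of every period, which is Day 5 of the preceding period when the visits coincide. No new review step is needed, since SoA footnote a already states: "All results must be reviewed prior to dosing on Day 1 of each treatment period". At W = 5 a resident woman's intervals then change from 1, 6 and 11 days to 1, 1 and 1.

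The cost is at most two extra urine tests per resident woman, on days when urinalysis is already scheduled, with no extra visit. The upper bound is 2 × 48 = 96 tests, if all 48 participants were resident women. A positive result needs serum confirmation (one blood sample) and could delay a dose; the washout is a minimum, so a delay is allowed. The amendment also needs ethics approval before it is implemented (Section 10.1.1).

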2.1. Study Rationale

Previous clinical studies of lasmiditan have used an immediate-release (IR) tablet formulation. An oral-disintegrating (OD) tablet has been developed to support pediatric development and for more convenient administration in adults, e.g., for those who have difficulty swallowing a tablet.

This study is intended to determine the bioequivalence, safety, and tolerability of a newly developed OD tablet of lasmiditan compared to the current IR tablet. Information on the acceptability and palatability of the OD tablet will also be collected during the study.

2.2. Background

Lasmiditan is a low-molecular-weight agonist of the 5-hydroxytryptamine (5-HT)_{1F} receptor with a nonvascular and primarily neural mechanism of action. It has a high affinity for the human 5-HT_{1F} receptor and a >440-fold selectivity for the human 5-HT_{1F} receptor relative to the 5-HT_{1B} receptor. Lasmiditan has high solubility and permeability.

Lasmiditan doses have been evaluated in healthy participants or patients with migraine across completed Phase 1, 2, and 3 clinical studies. Across these studies, single intravenous and single oral doses of lasmiditan were administered over a range of 0.1 mg to 400 mg. Multiple oral doses of 200 mg or 400 mg were administered orally once daily (QD) for 7 days. Cumulatively through 14 August 2018, approximately 4945 participants have received lasmiditan. The most frequently reported lasmiditan adverse events (AEs) in the 2 Phase 3 placebo-controlled studies, in which patients treated 1 migraine attack with oral lasmiditan (50, 100, or 200 mg) or placebo, were dizziness, paresthesia, somnolence, fatigue, and nausea, and the majority were mild or moderate in severity. Safety and tolerability in healthy participants were similar up to the highest dose of 400 mg administered as a single and multiple (QD for 7 days) dose, with drowsiness, dizziness, and paresthesia being the most frequently reported AEs. The majority of these were mild in severity, and none were severe.

In previous studies, following single oral dose administration of lasmiditan to healthy participants, lasmiditan was absorbed with a median time of maximum observed drug concentration (t_{max}) of 1.8 hours, and rapidly eliminated with a mean terminal half-life ($t_{1/2}$) of approximately 5.7 hours. Lasmiditan exposure increased in a dose-dependent manner that was considered to be approximately linear with dose over a clinical dose range of 50 to 200 mg. No accumulation of lasmiditan was previously observed with repeated QD dosing of 200 or 400 mg. Lasmiditan undergoes extensive hepatic and extrahepatic metabolism with ketone reduction to inactive metabolite 8 (M8) as the major biotransformation pathway.

